16.42 Sample Size

The one-stage design to be utilized is fully described in Section 16.21. A minimum of 22 evaluable patients will be accrued to this phase-II study unless undue toxicity is encountered. We anticipate accruing an additional 3 patients to account for ineligibility, cancellation, major treatment violation, or other reasons. Maximum projected accrual is therefore 25 patients. We anticipate pre-registering 40 patients to register a total of 25 patients necessary for the study design.

16.43 Accrual Time and Study Duration

We anticipate enrolling 25 patients and thus plan to finish accrual of patients in 1.5-2 years after opening the study, leaving year 5 for follow-up and analysis. Therefore, the overall study duration is expected to be 84 months.

16.44 Power and Significance Levels

Assuming the number of successes is binomially distributed, the significance level is 0.10 and the probability of declaring that this regimen warrants further studies (i.e. statistical power) under various success proportions and the probability of stopping accrual can be tabulated as a function of the true success proportion as shown in the following table.

If the true success proportion is ...	0.05	0.10	0.15	0.20	0.25
---------------------------------------	------	------	------	------	------

Then the probability of declaring that the regimen warrants further studies is...	0.09	0.38	0.66	0.85	0.94
---	------	------	------	------	------

16.45 Other Considerations

Adverse events observed in this study as well as scientific discoveries or changes in standard care will be taken into account in any decision to terminate the study.

16.5 Analysis Plan

The analysis for this trial will commence at the planned time points (see 16.2) and at the time the patients have become evaluable for the primary endpoint. Such decision will be made by the Statistician and Study chair, in accord with the Cancer Center Statistics (CCS) Standard Operating procedures, availability of data for secondary endpoints, and the level of data maturity. It is anticipated that the earliest date in which the results will be made available via a manuscript, abstract, or presentation format is when 22 patients have had definitive surgical treatment.

16.51 Primary Analysis: The primary analysis will be to estimate the pathologic complete response (pCR) rate observed at time of definitive surgery in breast cancer patients receiving preoperative ionizing radiation. All patients meeting eligibility criteria who have signed a consent form and who have begun treatment will be evaluable for the primary analysis.

16.511 Estimation: The proportion of successes (number of patients achieving pCR at time of definitive surgery) will be estimated by the number of successes divided by the total number of evaluable patients. Confidence intervals for the true success proportion will be calculated according to the approach of Duffy and Santner [74].

16.512 Over Accrual: If more than the target number of patients are accrued, the additional patients will not be used to evaluate the stopping rule or used in any decision making processes; however, they will be included in final point estimates and confidence limits.

16.52 Secondary Analyses

16.521 *Acute adverse events (up to 180 days post-RT):* All patients who were registered to the study and started treatment will be included in the acute adverse event analysis. An acute adverse event is an AE, regardless of attribution, that occurs up to 180 days post-RT. The maximum grade for each type of acute AE will be recorded for each patient. Data will be summarized as frequencies and relative frequencies. Additionally, the relationship of the adverse event(s) to the study treatment will be taken into consideration.

16.522 *Late adverse events:* All patients who were registered to the study and started treatment will be included in the late adverse event analysis. A late adverse event is an AE, regardless of attribution, that after one month post-RT and up to 5 years post-RT. The maximum grade for each type of late AE will be recorded for each patient. Data will be

summarized as frequencies and relative frequencies by treatment arm. Additionally, the relationship of the adverse event(s) to the study treatment will be taken into consideration.

- 16.523 *Locoregional control:* The cumulative incidence of locoregional recurrence will be estimated using a competing risks method (Gooley et al.). The competing risks will be distant breast cancer recurrence and death.
- 16.524 *Invasive disease-free survival:* i-DFS is defined as the time from registration until the time of disease recurrence or death due to any cause. The i-DFS will be estimated with a Kaplan-Meier estimator and curve. Estimates will be given for specific time points along with 95% CIs.
- 16.525 *Disease-free survival:* DFS is defined as the time from registration until the time of disease recurrence or death due to any cause. The DFS will be estimated with a Kaplan-Meier estimator and curve. Estimates will be given for specific time points along with 95% CIs.
- 16.526 *Cause specific survival:* The CSS will be estimated with a Kaplan-Meier estimator and curve. Estimates will be given for specific time points along with 95% CIs.
- 16.527 *Overall survival:* The OS will be estimated with a Kaplan-Meier estimator and curve. Estimates will be given for specific time points along with 95% CIs.

16.53 Exploratory Analyses:

- 16.531 *Quality of life:* The subscales of the BCTOS, elements from CTCAE-PRO, and other patient reported measures such as fatigue, breast pain, breast shape, and arm related morbidity outlined in the appendix will be summarized as the mean \pm SD and median (minimum value, maximum value). Scale score trajectories over time will be examined using stream plots and mean plots with standard deviation error bars overall. Analysis will include percent change from baseline using t-tests and generalized linear models to test for changes at each time point and non-zero slope respectfully.
- 16.532 *Cosmesis:* The values of the cosmesis instruments (patient self-reported and panel-assessed) will be summarized with the frequencies and confidence intervals of fair or poor cosmesis events at baseline, 2 years, and 5 years.
- 16.533 Tumor mutation signatures will be analyzed before and after radiotherapy as compared to pathologic information at the time of surgery. Continuous variable will be compared using unpaired t tests and monimal variables will be compared using contingency tables and Chi square analyses.
- 16.534 Pathologic changes due to preoperative radiotherapy observed at the time of definitive surgery will be described.

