2.2 Secondary Objectives

- 2.21 To evaluate acute and late toxicity with preoperative radiation including grade ≥ 2 pneumonitis.
- 2.22 To estimate the 5-year locoregional control, distant recurrence, invasive disease-free survival, cause-specific survival, and overall survival.

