7.11 Surgery

7.11.1 Surgical treatment will be done at the discretion of the treating surgeon.
7.11.2 Surgery will be done at 8 weeks after the completion of radiation.
Acceptable range is 4-16 weeks after.

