7.12 Endocrine therapy or chemotherapy

7.12.1 Systemic management would be done at the discretion of the treating medical oncologist after the surgery

8 Radiotherapy Dose Modifications Based on Adverse Events

This study has no pre-specified interruptions due to adverse events. Treatment interruptions are discouraged. No dose modifications should be done for treatment interruptions.

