10.22 Assessment of Attribution

Only G4 or G5 adverse events will require an attribution. Any change in the grade of an adverse event within the list of monitored AEs will be recorded and considered to be related to treatment. Any new adverse not listed occurring within the Radiated area or in close proximity will be graded and attribution defined by the study PI.

Events determined to be possibly, probably or definitely attributed to a medical treatment suggest there is evidence to indicate a causal relationship between the treatment and the adverse event.

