16.2 Primary and Secondary Endpoints

16.21 Primary Endpoint: The pathologic complete response (pCR) rate observed at time of definitive surgery in breast cancer patients receiving preoperative ionizing radiation. A residual tumor cancer burden 0-1 would be considered a pCR.³¹ All patients meeting eligibility criteria who have signed a consent form and who have begun treatment will be evaluable for the endpoint.

16.22 Secondary Endpoints:

16.221 Acute and late adverse events including grade ≥ 2 pneumonitis.

16.223 Locoregional control, invasive disease-free, distant recurrence, disease-free survival, cause-specific survival, overall survival.

The following definitions are used for the secondary endpoints of interest:

- *Pathologic complete response*: We defined a pathological complete response (pCR) as a residual tumor burden of 0-1 in the surgical specimen.³¹
- *Acute adverse events* (up to 180 days post-RT): any adverse event, regardless of attribution, that occurs in the first month post-RT.
- *Late adverse events* (up to 5 years post XRT): any adverse event that occurred after the first month post-RT and up to 5 years post-RT.
- *Ipsilateral breast tumor recurrence (IBTR)*: this is defined as local recurrence from trial registration as a first event at 5 years. IBTR is defined as both invasive and non-invasive breast cancer involving the same breast parenchyma as the original tumor.
- *Regional recurrence*: invasive breast cancer in the axilla, regional lymph nodes, chest wall, and skin of the ipsilateral breast at 5 years.
- *Distant recurrence*: metastatic cancer that has either been biopsy confirmed or clinically diagnosed as recurrent invasive breast cancer at 5 years.
- *Invasive disease-free survival*: this is defined as the time from study registration until the occurrence of one of the events in a composite endpoint. This endpoint includes invasive IBTR, regional invasive breast cancer recurrence, distant breast cancer recurrence, death due to any cause,
- *Disease-free survival*: this is defined as the time from study registration until the occurrence of one of the events in a composite endpoint. This endpoint includes any IBTR, regional invasive breast cancer recurrence, distant breast cancer recurrence, death due to any cause,

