18.0 Records and Data Collection Procedures

18.1 Submission Timetable

Initial Material(s)

CRF	Treatment (Compliance with Test Schedule Section 4.0)
Institutional Contacts	
Patient Eligibility	
Demographics	
On-Study	≤2 weeks after registration
Pathology of Ipsilateral Breast	
Adverse Events- Baseline	
Patient Status: Baseline	
Patient Assessment	
	*6 months after accrual
Off Treatment	Submit ≤2 weeks after registration if withdrawal/refusal occurs prior to beginning protocol therapy

Test Schedule Material(s)

CRF	End of Treatment	12 weeks post-RT / Observation Phase ⁴	Event Monitoring ⁵
Radiation Therapy	X		
Radiation Lumpectomy Therapy	X		
Patient Assessment	X	X	
Adverse Events Solicited	X	X	
Adverse Events: Other	X ²	X ²	
Off Treatment	X ²	X ²	
Patient Status Form	X	X	X
Specimen Submission: Tissue (Recurrence)		X ²	
Consent Withdrawal	X ²	X ²	
Lost to Follow-up	X ²	X ²	
Breast Radiotherapy Questionnaire ³	X	X	

- ¹ Complete at each evaluation during Active Treatment (see Section 4.0).
- ² When applicable
- ³ Survey will need to be entered manually if has not alternately been scanned or entered electronically
- ⁴ Active monitoring observation phase, Day 15 (+/- 3 days), D90 (+/- 1 month), D180 (+/- 2 months), D365 (+/- three months), annually for 4 years (+/- 6 months, total 5 years follow-up). If patient progresses within observation, they will move to the event monitoring phase where they will be followed until 5 years of follow-up information has been completed from the end of treatment time point.
- ⁵ If patient has a recurrence prior to being off radiation therapy for 5 years, continue to follow yearly.

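### The acute toxicity table in 16.521 runs through surgery with no split, so pain, fibrosis and lymphedema mix radiation and surgical effects, and 16.22 defines the acute window differently

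*Combined protocol and SAP*

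**What the plan says.** - **Objective (2.2, item 2.21):** "To evaluate acute and late toxicity with preoperative radiation including grade ≥ 2 pneumonitis".
- **Acute analysis (16.521):** "An acute adverse event is an AE, regardless of attribution, that occurs up to 180 days post-RT". The summary is the highest grade per patient for each type of event. A closing sentence says that relationship to treatment will be considered, but gives no method.
- **Acute definition (16.22):** the label gives 180 days, but the text reads "any adverse event, regardless of attribution, that occurs in the first month post-RT".
- **Late definition (16.22, repeated in substance in 16.522):** "any adverse event that occurred after the first month post-RT and up to 5 years post-RT".
- **Surgery (7.11):** planned 8 weeks after radiation ends. "Acceptable range is 4-16 weeks after".
- **Systemic therapy (7.12):** "Systemic management would be done at the discretion of the treating medical oncologist after the surgery". No start date is given.
- **Monitored terms (10.4):** pain, radiation dermatitis, hyperpigmentation, hypopigmentation, fibrosis, lymphedema and pneumonitis, graded at baseline and at each evaluation.
- **Attribution (10.22):** required only for grades 4 and 5. A grade change in a monitored term "will be recorded and considered to be related to treatment". The PI assigns attribution to new unlisted events in or near the irradiated area.
- **Assessments (18.1):** solicited adverse events are collected at End of Treatment and in the observation phase, with visits at Day 15 (±3 days), D90 (±1 month) and D180 (±2 months).

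**The concern.** The objective concerns toxicity of radiation given before surgery. The table meant to answer it covers a period in which breast surgery also takes place. A maximum grade keeps only the worst value for each term. If post-operative pain or lymphedema is graded higher than anything seen after radiation, the post-operative grade is the one reported, and 10.22 counts it as treatment-related. A reader of the acute table could not then tell what patients experienced from radiation before the operation. With at most 25 patients, one such patient moves a reported rate by 1/25 = 4 percentage points. The design does provide a pre-surgery interval with scheduled assessments, but the planned summary does not show it separately.

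**Working it through.** The plan gives no figure for this endpoint. Its only computed design figures, the pCR table in 16.44, reproduce as P(X ≥ 3) with X ~ Binomial(22, p): 0.0948, 0.3800, 0.6618, 0.8455 and 0.9394, against 0.09, 0.38, 0.66, 0.85 and 0.94. Nothing below depends on them.

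**1. Share of the 180-day window after surgery.** Surgery day = 7 × weeks (7.11). Share = (180 − surgery day)/180. Days are counted from the end of radiation.
- Week 4: day 28; (180 − 28)/180 = 152/180 = 84%.
- Week 8: day 56; (180 − 56)/180 = 124/180 = 69%.
- Week 16: day 112; (180 − 112)/180 = 68/180 = 38%.

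**2. Where the visits in 18.1 fall against surgery on days 28 to 112.** This assumes 30-day months and visit days counted from the end of radiation.
- End of Treatment, and Day 15 (days 12 to 18): always before surgery.
- D90 (days 60 to 120): either side. Extremes are 60 − 112 = −52 (52 days before) and 120 − 28 = +92 (92 days after).
- D180 (days 120 to 240): always after surgery.

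Radiation-only grades are therefore collected, and the maximum pools them with post-operative ones.

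**3. Which terms are exposed.** The maximum is taken within each type of event, so post-operative pain cannot replace a dermatitis or pneumonitis grade. Of the seven terms in 10.4, pain, fibrosis and lymphedema can plausibly arise from surgery; the background section itself names lymphedema as a post-operative complication. That the other four are less exposed is a judgement, not a figure from the documents.

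**4. Whether attribution separates the sources.** For a grade 1 to 3 change in a monitored term, 10.22 requires no attribution and presumes relatedness. The closing sentence of 16.521 has no attribution data to draw on that would isolate surgery for these terms.

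**5. The competing definition.** Take one month as 28 to 31 days.
- If acute means the first month, post-operative days in the acute window are at most 28 − 28 = 0 to 31 − 28 = 3.
- The late window then begins at one month, so almost all post-operative time falls there. Section 16.522 also ignores attribution and has no split at surgery.
- If acute means 180 days, the acute and late windows overlap by 180 − 31 = 149 to 180 − 28 = 152 days, and one event can count in both.

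**6. Illustration only.** The documents give no event rates. Assume, for one term, a 10% rate from radiation and an independent post-operative rate s. The observed rate is 1 − 0.90 × (1 − s): 14.5% at s = 5% and 37% at s = 30%.

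**The case against.** Reporting adverse events regardless of attribution is ordinary practice, and a profile of radiation followed by surgery is a legitimate target. The plan clearly cares about post-operative harm: 16.62 lists in-field wound infection, and 2.32 lists unplanned surgical intervention. The table is descriptive, secondary and tied to no test, and safety decisions run through 16.62, which considers events at least possibly related to treatment. The example worksheet in 10.3 also records event dates and relationship to the research. All of this stands, and it is why the combined table should be kept. It does not supply a pre-surgery result for an objective worded around preoperative radiation, and the presumption in 10.22 remains. If the sponsor intends the whole regimen as the target, the plan should say so.

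A reader might infer more than the documents support:
- **That 38% to 84% of reported events are surgical.** The figures are shares of days.
- **That radiation-only toxicity is not collected.** End of Treatment and Day 15 always precede in-range surgery.
- **That the whole acute profile is compromised.** The maximum is per type of event, and pneumonitis, the one event 2.21 names, is less exposed.
- **That systemic therapy certainly contributes.** It follows surgery and may start inside the window, but no date is given.
- **That 180 days is settled.** Section 16.22 says otherwise in its text.

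The Section 4.0 schedule grid is not visible in the text reviewed, so an assessment tied to surgery cannot be excluded. Such a visit would not by itself split the maximum grade.

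**Conclusion.** The point holds as a reporting gap that should be closed before analysis. Under the 180-day definition, every patient operated on in the permitted range contributes post-operative time to the acute table: 69% of the window at planned timing, 38% to 84% across the range. The summaries of pain, fibrosis and lymphedema then mix radiation and surgical effects that the required attribution data cannot separate at grades 1 to 3. Under the first-month definition the same mixing passes to the late table, so choosing between the definitions does not remove it. The size of any distortion in reported rates cannot be estimated from the documents. The conclusion assumes surgery within 4 to 16 weeks and no split defined in material that is not visible. It does not bear on the pCR analysis.

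**What to change.** 1. Reconcile the acute window between 16.22 and 16.521, and settle its overlap with the late window in 16.522.
2. Keep the combined table in 16.521 and add the maximum grade per term for two periods:
   - (a) start of radiation to the day before surgery, labelled as pre-surgery (radiation-only) toxicity, using End of Treatment, Day 15 and any D90 assessment made before surgery;
   - (b) surgery to the end of the window, read against the last pre-surgery grade, with events after the start of systemic therapy flagged.
3. Report pneumonitis over the full window as well, so that later cases are not lost from the radiation result.
4. Keep patients who start radiation but never have surgery in period (a) to the end of the window.
5. Apply the same before/after-surgery flag to the late table.

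The cost is SAP wording, one derived variable and one more table. The adverse event date is on the worksheet in 10.3, and the surgery date is needed for the primary completion date in 16.7; the systemic-therapy flag also needs that therapy's start date. No visit or treatment changes. The downside is that period (a) lasts about 28 to 112 days depending on when surgery takes place, so its length should be reported beside the grades.

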13.0 Treatment/Follow-up Decision at Evaluation of Patient

Follow-up data will be collected and entered after the observation phase outlined in section 4.0. If the patient is still alive after 5 years have elapsed from the on-study date, no further follow-up is required by this protocol.

- 13.1 Patients who have a recurrence while receiving therapy or during observation will go to the event-monitoring phase and be followed
- 13.2 Patients who discontinue treatment or observation for reasons other than recurrence will go to the event-monitoring phase and be followed
- 13.3 Patients who will not receive any radiation treatment or who will receive radiation treatment elsewhere will move to event monitoring phase.
- 13.4 A patient is deemed *ineligible* if after registration, it is determined that at the time of registration, the patient did not satisfy each and every eligibility criteria for study entry. The patient may continue treatment off-protocol at the discretion of the physician as long as there are no safety concerns, and the patient was properly registered. The patient will go directly to the event-monitoring phase of the study (or off study, if applicable).

If the patient received treatment, all data up until the point of confirmation of ineligibility must be submitted. Event monitoring will be required per Section 18.0 of the protocol.

If the patient never received treatment, on-study material and the End of Active Treatment/Cancel Notification Form must be submitted. No further data submission is necessary.

- 13.5 A patient is deemed a *cancel* if he/she is removed from the study for any reason before any study treatment is given. On-study material and the End of Active Treatment/Cancel Notification Form must be submitted. No further data submission is necessary.

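### Late adverse events are summarised as crude proportions of all treated patients with no allowance for time under AE observation, which modestly understates 5-year late toxicity

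*Combined protocol and SAP*

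**What the plan says.** Section 16.2 defines a late adverse event as "any adverse event that occurred after the first month post-RT and up to 5 years post-RT". Section 16.522 sets the denominator: "All patients who were registered to the study and started treatment will be included in the late adverse event analysis". The measure per patient is the worst grade: "The maximum grade for each type of late AE will be recorded for each patient". The results are then "summarized as frequencies and relative frequencies by treatment arm", although the trial has one arm. No onset time, censoring rule or exposure adjustment is given.

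The neighbouring items do allow for incomplete follow-up. In 16.523, "The cumulative incidence of locoregional recurrence will be estimated using a competing risks method", with distant recurrence and death as the competing events. Items 16.524 to 16.527 use Kaplan-Meier estimates with 95% confidence intervals.

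On follow-up, 13.1 and 13.2 say that patients who recur, and patients who stop treatment or observation for another reason, "will go to the event-monitoring phase and be followed". Footnote 4 of the 18.1 table repeats this for recurrence: "If patient progresses within observation, they will move to the event monitoring phase". In that table both AE forms (solicited and other) are marked at end of treatment and in the observation phase. Under event monitoring only the Patient Status Form is marked.

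**The concern.** A patient who leaves observation at, say, 18 months with no late AE of a given type stays in the denominator for the 5-year summary and adds nothing to the numerator. The unobserved 3.5 years are treated as event-free. The same applies to a patient who is lost, who withdraws, or who has not reached 5 years when the table is produced. The error runs in one direction, towards a more favourable safety profile.

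Late toxicity, with grade 2 or higher pneumonitis named, is a secondary objective (2.21). Fibrosis, lymphedema and pneumonitis are solicited at each evaluation (10.4). Grade 2 and 3 events of these kinds are the ones with no marked form after the move to event monitoring.

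**Working it through.** **The plan's own figures.** The documents state no late-AE rate, recurrence rate or loss rate, so there is no late-AE figure to reproduce. The only design figures are the pCR operating characteristics in 16.44. With at least 3 successes in 22 and true rates of 0.05, 0.10, 0.15, 0.20 and 0.25, the exact binomial gives 0.0948, 0.3800, 0.6618, 0.8455 and 0.9394. The plan states 0.09, 0.38, 0.66, 0.85 and 0.94. These agree and are not in question.

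**Inputs.** The window is 1 month to 5 years, T = 4.92 years (16.2). The maximum N is 25 (16.42). The true 5-year risk F and the share G leaving AE follow-up by 5 years are assumptions.

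**Formula.** With constant hazards, the AE hazard is a = −ln(1−F)/T and the exit hazard is g = −ln(1−G)/T. Only events before exit are seen, so

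expected crude proportion = a/(a+g) × [1 − (1−F)(1−G)].

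T cancels. For F = 0.20 and G = 0.20 the hazards are equal: 0.5 × (1 − 0.64) = 0.180. For F = 0.20 and G = 0.30: 0.2231/(0.2231 + 0.3567) × (1 − 0.56) = 0.385 × 0.44 = 0.169.

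| Share leaving AE follow-up (assumed) | Crude, true risk 20% | Relative shortfall | Patients missed of 25 |
|---|---|---|---|
| 2% | 19.8% | 1% | 0.05 |
| 5% | 19.5% | 2.4% | 0.12 |
| 10% | 19.0% | 5% | 0.25 |
| 20% | 18.0% | 10% | 0.5 |
| 30% | 16.9% | 15% | 0.8 |

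The relative shortfall is nearly the same at true risks of 10% and 30%. At 30%, the crude figure is 27.1% with 20% exits and 25.5% with 30% exits. That last cell is 7.5 − 6.38 = 1.1 patients of 25, the only one in the range above a single patient.

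**Death.** In 20,000 simulated trials of 25 patients with deaths but no other exits, the crude proportion and the Aalen-Johansen cumulative incidence were identical in every run (both 19.5% with 5% deaths, both 18.0% with 20% deaths). With 5% deaths and 20% other exits, the true cumulative incidence is 19.5%, the crude mean 17.7% and the Aalen-Johansen mean 19.6%. The estimator removes the shortfall, and the shortfall comes from the other exits.

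**Incomplete follow-up at reporting.** Assume uniform accrual over 2 years (the upper end of 16.43), entry taken as the end of radiotherapy, F = 0.20 and no exits. The expected crude proportion is then 5.1% at 2.25 years after opening, 8.3% at 3 years, 16.3% at 5 years and 20.0% at 7 years. Read as 5-year risk, an early table would be low by much more than any exit effect above.

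**The case against.** Several counter-arguments are sound.

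- A reader might infer that death also causes understatement. It does not. With death as the competing event and no other censoring, the crude proportion is the cumulative incidence.
- A reader might infer that the plan stops AE collection at recurrence. No sentence says so. The inference rests on unmarked cells in the 18.1 table, and the grid of the section 4.0 schedule is not in the text available here, only its footnotes. Serious (grade 4 and 5) events and possibly related late deaths stay reportable under 10.3 and 10.5 with no stated end at recurrence, and follow-up runs to 5 years. The possible gap is in lower grades.
- Worst grade is kept, so an event recorded before exit still counts. Only patients with no earlier event of that type are affected.
- Recurrence can be handled in two ways. In 16.523 distant recurrence is a competing event. If recurrence were competing for late AEs too, exits at recurrence would cause no bias, and only loss, withdrawal and incomplete follow-up would remain. Censoring at recurrence assumes that exit is unrelated to later AE risk. Retreatment after recurrence (11.2.4) can itself cause AEs, which 16.522 counts whatever their attribution.
- Objective 2.21 is to evaluate toxicity, not to estimate a 5-year risk, and a worst-grade table is a fair description of what was seen. Section 16.5 also ties release of results to data maturity.
- Imprecision is larger than the bias. At a true 20% with N = 25 the standard error is √(0.2 × 0.8/25) = 8 points, and 5 of 25 has an exact 95% interval of about 7% to 41%.

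These points limit the claim and its size. They do not remove the bias from loss, withdrawal and incomplete follow-up, and they do not explain why 5-year late toxicity is treated differently from the other 5-year endpoints in 16.52.

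**Conclusion.** The point holds in a limited form. As an estimate of 5-year risk, the 16.522 proportion is biased downward, because patients who are lost, withdrawn, moved to event monitoring or not yet at 5 years, with no earlier event of that type, count as event-free for unobserved time. For moves to event monitoring, this depends on AE forms stopping there, which is inferred.

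The relative shortfall is about 1% to 15% for 2% to 30% exits. At a true risk of 20% that is under one patient in 25. It rests on constant hazards and on rates that the documents do not give; earlier AE onset would shrink it. It would be larger only if an early table were read as 5-year risk.

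The documents do not support a stronger reading, that the safety conclusions or trial decisions are compromised. The pCR rule does not use this proportion, and the stopping rule in 16.62 works on patient counts. This is a cheap improvement of low severity.

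**What to change.** Keep the maximum-grade table and drop the reference to treatment arms. Beside it:

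1. Report the cumulative incidence of first late grade ≥2 AE, first late grade ≥3 AE, and grade ≥2 pneumonitis. Treat death as a competing event, censor at the last AE assessment, and show numbers at risk at 1, 2 and 5 years.
2. State whether recurrence is a competing event, as distant recurrence is in 16.523, or a censoring event. Show the other choice as a sensitivity analysis.
3. State in 18.1 whether the AE forms continue in event monitoring.

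The cost is a little more analysis, with no new visits or patients. There are two limits. Onset of solicited events may be datable only to the scheduled visit (annual, ±6 months, in later years), because an AE date appears only on the example worksheet in section 10.3. Intervals will also be wide at N = 25.
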